3.3 Budget

Please refer to attached Budget for details.

Chapter 4: Supplementary & Supporting Materials

4.1 OSDI

Ocular Surface Disease Index[®] (OSDI[®])²

Ask your patients the following 12 questions, and circle the number in the box that best represents each answer. Then, fill in boxes A, B, C, D, and E according to the instructions beside each.

Have you experienced any of the following during the last week ?	All of the time	Most of the time	Half of the time	Some of the time	None of the time
1. Eyes that are sensitive to light?	4	3	2	1	0
2. Eyes that feel gritty?	4	3	2	1	0
3. Painful or sore eyes?	4	3	2	1	0
4. Blurred vision?	4	3	2	1	0
5. Poor vision?	4	3	2	1	0

Have problems with your eyes limited you in performing any of the following during the last week ?	All of the time	Most of the time	Half of the time	Some of the time	Non of th time	e	N/A
6. Reading?	4	3	2	1	0		N/A
7. Driving at night?	4	3	2	1	0		N/A
8. Working with a computer or bank machine (ATM)?	4	3	2	1	0		N/A
9. Watching TV?	4	3	2	1	0		N/A

							_
9	Subtotal	score	for	answers	6 1	to 9	

Subtotal score for answers 1 to 5

(A)

(B)

Have your eyes felt uncomfortable in any of the following situations during the last week ?	All of the time	Most of the time	Half of the time	Some of the time	-	None of the time	N/A
10. Windy conditions?	4	3	2	1		0	N/A
11. Places or areas with low humidity (very dry)?	4	3	2	1		0	N/A
12. Areas that are air conditioned?	4	3	2	1		0	N/A

Subtotal score for answers 10 to 12 (C)

Add subtotals A, B, and C (D = sum of scores for all question	
Total number of question (do not include questions an	

[figure not shown]
Please turn over the questionnaire to calculate the patient's final OSDI® score.

Evaluating the OSDI[®] Score¹

The OSDI[®] is assessed on a scale of 0 to 100, with higher scores representing greater disability. The index demonstrates sensitivity and specificity in distinguishing between normal subjects and patients with dry eye disease. The OSDI[®] is a valid and reliable instrument for measuring dry eye disease (normal, mild to moderate, and severe) and effect on vision-related function.

Assessing Your Patient's Dry Eye Disease^{1, 2}

Use your answers D and E from side 1 to compare the sum of scores for all questions answered (D) and the number of questions answered (E) with the chart below.* Find where your patient's score would fall. Match the corresponding shade of red to the key below to determine whether your patient's score indicates normal, mild, moderate, or severe dry eye disease.

1. Data on file, Allergan, Inc.

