1.4 Summary and Hypothesis

Given the aforementioned data and relative lack of prospective studies regarding the use of MGX/IPL in patients with DED, we propose a prospective, randomized, case-controlled clinical pilot study to examine the efficacy of IPL for both subjective and objective measures. 20 patients with DED will be recruited, and will be randomly assigned to one of two groups: MGX alone, or MGX with IPL, and will undergo treatment every 4-6 weeks for 4 total treatment. Subjectively, participants will be scored using dry eye symptom questionnaires, including the OSDI, prior to treatment and post-treatment. Objective measures at baseline and at the end of the study will include tear cytokine levels, impression cytology for inflammatory markers, meibography, tear osmolarity, and ocular microbiome testing (see Chapter 2).

We hypothesize that use of MGX with IPL will lead to greater improvement in subjective dry eye symptoms, improved objective meibomian gland measures, and an upregulation in tear cytokines such as TGF-B1 and downregulation of inflammatory markers, such as IL-10, and improvement of ocular microbiome load, as compared to participants treated with MGX alone.

Given the lack of adverse effects reported in the literature, we do not anticipate study participants will experience adverse effects with proper performance of the IPL and testing procedures. For IPL subjects, masking using IPL-aid for both eyes will be used to protect the ocular structures. After Fitzpatrick skin type assessment, test application of IPL will be performed at the right preauricular skin and evaluated for erythema or skin change prior to

proceeding with the rest of the IPL application. We will record all events and include them in our analyses.

Chapter 2: Study Overview and Design

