2.3 Participant Randomization

Once inclusion criteria have been met, patients will be randomized to one of two groups using a random number generator. 10 patients will be randomized to the control group, in which they will receive MGX every 4-6 weeks; and 10 patients will be randomized to the treatment group, in which they will receive MGX and IPL every 4-6 weeks. Biomarker and microbiome labs and data analyzer will be masked to treatment group.

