2.4 Data Collection and Analysis

Appointment 1/Baseline. Data will be collected on the participants first visit ("baseline") and will include the following: OSDI, visual acuity, slit lamp imaging, lissamine green staining, fluorescein, tear film break up time (TBUT), Schirmers 5 minute with anesthesia osmolarity, meibography, Keratograph5 redness evaluation, Lipiview lipid tear film thickness, , tear cytokine evaluation and impression cytology (for flow cytometry of labeled cells for inflammatory markers), and tear sample for ocular microbiome testing.

number identifier, and their data will be entered into an Excel Document ("data file") and RedCap database which will be kept on a secure server at Mayo Clinic Arizona.

[figure not shown]
At appointment 1, participants will receive the initial treatment of either MGX or MGX+IPL. At appointment 1, participants will be given Tobramycin-Dexamethasone ophth soln to use BID topically OU for 2 days, and told to avoid UV exposure for 3 weeks.

Appointment 2. 4-6 weeks after appointment 1, at appointment 2, participants will be evaluated using OSDI, visual acuity, Icare tonometry, slit lamp imaging, lissamine green staining, fluorescein staining. This data will be entered into the data file. Participants will receive their second treatment of either MGX or MGX+IPL. At appointment 2, participants will be given Tobramycin-Dexamethasone ophth soln BID for 2 days, and told to avoid UV exposure for 3 weeks

Appointment 3. 4-6 weeks after appointment 2, at appointment 3, participants will be evaluated using OSDI, visual acuity, Icare tonometry, slit lamp imaging, lissamine green staining, fluorescein staining. This data will be entered into the data file. Participants will receive their second treatment of either MGX or MGX+IPL. At appointment 3, participants will be given Tobramycin-Dexamethasone ophth soln BID for 2 days, and told to avoid UV exposure for 3 weeks

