Appointment 4. 4-6 weeks after appointment 3, at appointment 4, participants will be evaluated with the following: OSDI, visual acuity, slit lamp imaging, lissamine green staining, fluorescein, tear film break up time (TBUT), Schirmers 5 minute with anesthesia osmolarity, meibography, Keratograph5 redness evaluation, Lipiview lipid tear film thickness, , tear cytokine evaluation and impression cytology (for flow cytometry of labeled cells for inflammatory markers), and tear sample for ocular microbiome testing. Participants will receive their final treatment of either MGX alone or MGX + IPL. At appointment 4, participants will be given Tobramycin-Dexamethasone ophth soln BID for 2 days, and told to avoid UV exposure for 3 weeks. (Data from Vegunta et al (2016) [19] proved that 3 treatments alone are sufficient to produce a symptomatic MGX/IPL response with improvement of dry eye symptoms and signs. We did not expect that subjects would be compliant to return for a 5th appointment if there was no treatment being performed at that visit.)

Data Analysis. After the completion of 4 treatments, and the collection of data as outlined above, data will be analyzed using statistical methods for changes to the aforementioned tests. The analysis will be conducted by a research trainee who will be blinded to the participant groups. That is, they will receive the identifiers "Group 1" vs "Group 2", without the identification of which group received MGX/IPL vs MGX alone.

ÌPL)

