3.1 Subjective Parameters

Ocular Surface Disease Index (OSDI). OSDI is the National Eye Institute Visual Functioning Questionnaire and has been proven to be valid and reliable instrument for assessing DED. A copy has been attached in Chapter 4. The range of results is 2-100. We hypothesize a decrease in OSDI levels with MGX/IPL versus MGX alone. Cost for OSDI is estimated at \$20 for each test and will be bundled into OPH EST LIMITED EXAM CPT (see 3.3 below). OSDI Survey is included in Chapter 4.1.

QOL Survey.

Cost for QOL is estimated at \$20 for each test and will be bundled into OPH EST LIMITED EXAM CPT (see 3.3 below). QOL Survey is included in Chapter 4.2.

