4.2 QOL Survey

THE WORLD HEALTH ORGANIZATION QUALITY OF LIFE (WHOQOL) -BREF

The World Health Organization Quality of Life (WHOQOL)-BREF

© World Health Organization 2004

All rights reserved. Publications of the World Health Organization can be obtained from Marketing and Dissemination, World Health Organization, [name] ([contact]; [contact]; email: [contact]). Requests for permission to reproduce or translate WHO publications—whether for sale or for noncommercial distribution—should be addressed to Publications, at the above address ([contact]; email: [contact]).

The designations employed and the presentation of the material in this publication do not imply the expression of any opinion whatsoever on the part of the World Health Organization concerning the legal status of any country, territory, city or area or of its authorities, or concerning the delimitation of its frontiers or boundaries. Dotted lines on maps represent approximate border lines for which there may not yet be full agreement.

The mention of specific companies or of certain manufacturers' products does not imply that they are endorsed or recommended by the World Health Organization in preference to others of a similar nature that are not mentioned. Errors and omissions excepted, the names of proprietary products are distinguished by initial capital letters.

The World Health Organization does not warrant that the information contained in this publication is complete and correct and shall not be liable for any damages incurred as a result of its use.

WHOQOL-BREF

The following questions ask how you feel about your quality of life, health, or other areas of your life. I will read out each question to you, along with the response options. **Please choose the answer that appears most appropriate.** If you are unsure about which response to give to a question, the first response you think of is often the best one.

Please keep in mind your standards, hopes, pleasures and concerns. We ask that you think about your life **in the last four weeks**.

		Very poor	Poor	Neither poor nor good	Good	Very good
1.	How would you rate your quality of life?	1	2	3	4	5

		Very dissatisfied	Dissatisfied	Neither satisfied nor dissatisfied	Satisfied	Very satisfied
2.	How satisfied are you with your health?	1	2	3	4	5

The following q	juestions ask abo	ut how muc	h you have	experienced	certain th	ings in the last
four weeks.						

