		Not at all	A little	A moderate amount	Very much	An extreme amount
3.	To what extent do you feel that physical pain prevents you from doing what you need to do?	5	4	3	2	1
4.	How much do you need any medical treatment to function in your daily life?	5	4	3	2	1
5.	How much do you enjoy life?	1	2	3	4	5
6.	To what extent do you feel your life to be meaningful?	1	2	3	4	5

		Not at all	A little	A moderate amount	Very much	Extremely
7.	How well are you able to concentrate?	1	2	3	4	5
8.	How safe do you feel in your daily life?	1	2	3	4	5
9.	How healthy is your physical environment?	1	2	3	4	5

	-		1			
		Not at all	A little	Moderately	Mostly	Completely
10.	Do you have enough energy for everyday life?	1	2	3	4	5
11.	Are you able to accept your bodily appearance?	1	2	3	4	5
12.	Have you enough money to meet your needs?	1	2	3	4	5
13.	How available to you is the information that you need in your day-to-day life?	1	2	3	4	5
14.	To what extent do you have the opportunity for leisure activities?	1	2	3	4	5

The following questions ask about how completely you experience or were able to do certa	ain
things in the last four weeks.	

		Very poor	Poor	Neither poor nor good	Good	Very good
15.	How well are you able to get around?	1	2	3	4	5

		Very dissatisfied	Dissatisfied	Neither satisfied nor dissatisfied	Satisfied	Very satisfied
16.	How satisfied are you with your sleep?	1	2	3	4	5
17.	How satisfied are you with your ability to perform your daily living activities?	1	2	3	4	5
18.	How satisfied are you with your capacity for work?	1	2	3	4	5
19.	How satisfied are you with yourself?	1	2	3	4	5

20.	How satisfied are you with your personal relationships?	1	2	3	4	5
21.	How satisfied are you with your sex life?	1	2	3	4	5
22.	How satisfied are you with the support you get from your friends?	1	2	3	4	5
23.	How satisfied are you with the conditions of your living place?	1	2	3	4	5
24.	How satisfied are you with your access to health services?	1	2	3	4	5
25.	How satisfied are you with your transport?	1	2	3	4	5

The following question refers to how often you have felt or experienced certain things in the last four weeks.

		Never	Seldom	Quite often	Very often	Always
26.	How often do you have negative feelings such as blue mood, despair, anxiety, depression?	5	4	3	2	1

Do you have any comments about the assessment?

[The following table should be completed after the interview is finished]

		Equations for commuting domain scores	Raw score	Transformed scores*	

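### The only instruction for giving the OSDI has staff ask the questions and circle the answers, and the stated masking does not cover those staff: an avoidable, cheaply removed source of interviewer bias

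*Combined protocol and SAP*

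**What the plan says.** **Mode of administration.** Section 1.4 says that "participants will be scored using dry eye symptom questionnaires, including the OSDI, prior to treatment and post-treatment", and Section 2.4 says of appointments 2 and 3 that "participants will be evaluated using OSDI, visual acuity, Icare tonometry, slit lamp imaging, lissamine green staining, fluorescein staining". The OSDI is also in the lists for appointments 1 and 4. None of this text says who gives the form or whether the participant fills it in. Section 3.1 points to the copy in Section 4.1, and that form instructs staff: "Ask your patients the following 12 questions, and circle the number in the box that best represents each answer".

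**Quality of life.** The WHOQOL-BREF in Section 4.2 is the interview wording: "I will read out each question to you, along with the response options", and later "The following table should be completed after the interview is finished". Sections 2.5 and 3.1 name a QOL survey, but none of the four appointment lists in Section 2.4 includes it.

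**Masking.** Section 2.3: "Biomarker and microbiome labs and data analyzer will be masked to treatment group". Section 2.4: "The analysis will be conducted by a research trainee who will be blinded to the participant groups". Clinic staff and participants are not mentioned. Section 7.0 describes MGX only for the control arm, with no sham IPL.

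**Expected direction.** Section 3.1: "We hypothesize a decrease in OSDI levels with MGX/IPL versus MGX alone".

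**The concern.** A symptom score is open to influence at two points: what the participant says, and what is written down. If a staff member asks the question and chooses the category that best fits the reply, both points pass through that person. If that person knows the arm and expects IPL to help, the error can differ between arms.

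Masking the analyst as Group 1 and Group 2 does not help, because it acts after the answers are recorded. Nor can a comparison of 10 with 10 separate a recorder effect from a treatment effect.

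The OSDI matters here because it is the only symptom measure in all four appointment lists, and symptom improvement is among the hypotheses in Section 1.4. The plan designates no primary endpoint, so the OSDI cannot be called one, but it is clearly a comparison the trial intends to report.

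**Working it through.** The plan gives no figure to reproduce. Section 2.5 holds only a placeholder for the power calculation, with no alpha, SD or target difference. The check is a reading of the passages together, followed by arithmetic for scale.

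**1. Does the body override the form?** No. Sections 1.4, 2.4 and 3.1 say that participants are scored or evaluated with the OSDI and refer to the attached copy. None provides for self-completion. Someone following the plan as written has only the form's instruction to go by.

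**2. Are the people recording the OSDI covered by masking?** Not by any stated provision. Those listed are two kinds of laboratory and the analyst, all of whom work on material already collected. The OSDI is taken at the visits at which MGX or MGX plus IPL is delivered, so the staff present may know the arm.

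**3. Does the same hold for the WHOQOL-BREF?** In part. The form has an interviewer read the questions aloud, but asks the respondent to choose the answer. Circling by staff is explicit only on the OSDI. With no scheduled visit, there is at present no QOL assessment to which the point applies.

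**4. OSDI step size.** Inputs from Section 4.1: 12 items scored 0 to 4, total expressed on 0 to 100, items 6 to 12 may be marked N/A, and the score uses the number of items answered. With E items answered the maximum raw sum is 4E, so one category on one item is 100/(4E) points.

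- E = 12: 100/48 = 2.08 points
- E = 9: 100/36 = 2.78 points

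With all 12 answered, one category on three items is 3 × 2.083 = 6.25 points, and on six items 12.5 points. The number of items shifted is an assumption.

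**5. What such a shift would do to a test.** Assumptions: no true effect, 10 per arm, two-sided 5% two-sample t test on 18 df (critical value 2.101), and an SD of 15, 20 or 25 points. A shift of b points in one arm only gives noncentrality b / (SD × √(2/10)). For b = 6.25 and SD = 20 this is 6.25 / (20 × 0.4472) = 0.70.

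| Shift b (points) | SD 15 | SD 20 | SD 25 |
|---|---|---|---|
| 0 | 5.0% | 5.0% | 5.0% |
| 3 | 7.1% | 6.2% | 5.7% |
| 6.25 | 14.3% | 10.2% | 8.3% |
| 12.5 | 42.2% | 26.3% | 18.5% |

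Entries are false-positive rates. They show how sensitive a trial of this size would be to a given shift. They do not estimate the shift that would occur.

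**The case against.** The strongest reply is that the interview wording is the publishers' printed text on forms attached as supporting material, and that the protocol's own text names no interviewer. On that view the plan is silent rather than faulty. This stands to the extent that the plan nowhere makes a deliberate choice of staff interview. It does not remove the point, because Section 3.1 includes the form by reference and nothing else tells staff how to administer it.

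Other parts of the reply also stand:

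- A reader might infer that the interviewers are known to be unmasked. The documents do not say so. They list who is masked, omit clinic staff, and never name who gives the form. The supportable statement is that these staff may know the arm.
- A reader might infer that staff circle the answers on both forms at every visit. That is stated for the OSDI only, and the WHOQOL-BREF is unscheduled.
- The OSDI comes first in each appointment list and treatment is described after the evaluations, so the intended order may already be right. The order is not required, though, and it does not settle who records the answers.
- The items have fixed frequency categories, which limits a recorder's discretion.
- Participants know their own arm, and that is probably the larger bias. Self-completion does not touch it. How much the interviewer adds cannot be derived from the documents.

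**Conclusion.** The point holds as a cheap improvement. As written, the plan lets staff who may know the arm ask for and record a subjective outcome with a directional hypothesis, and its masking provisions act too late to protect it.

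The size is unknown. The only document-based figure is the step of 2.1 OSDI points per item category with all 12 items answered, and more with fewer. The false-positive rates above rest on an assumed SD and an assumed shift.

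It would go too far to conclude that the OSDI comparison is biased by a known amount, or that changing the mode of completion would make it a masked comparison. The documents support neither. The change removes the interviewer part only and alters no sample size or power figure.

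**What to change.** In Sections 2.4 and 4.1, state that in both arms and at every appointment the participant completes the OSDI alone on arrival, before any examination, discussion of response or treatment. Staff check only for blank items. Where the form has to be read aloud, staff read it verbatim and record that they did so. Put the same statement in Section 4.2 if the WHOQOL-BREF is added to the appointment lists.

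Paper is enough. Section 2.4 describes entering data into an Excel file and a RedCap database, not an electronic questionnaire, so no existing electronic form should be assumed.

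Cost: a short addition to the text, a change to the instruction wording on the form, and probably a few more blank items, which the check for blanks should limit. No extra visits or participants are needed.

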4.2 QOL Survey

THE WORLD HEALTH ORGANIZATION QUALITY OF LIFE (WHOQOL) -BREF

The World Health Organization Quality of Life (WHOQOL)-BREF

© World Health Organization 2004

All rights reserved. Publications of the World Health Organization can be obtained from Marketing and Dissemination, World Health Organization, [name] ([contact]; [contact]; email: [contact]). Requests for permission to reproduce or translate WHO publications—whether for sale or for noncommercial distribution—should be addressed to Publications, at the above address ([contact]; email: [contact]).

The designations employed and the presentation of the material in this publication do not imply the expression of any opinion whatsoever on the part of the World Health Organization concerning the legal status of any country, territory, city or area or of its authorities, or concerning the delimitation of its frontiers or boundaries. Dotted lines on maps represent approximate border lines for which there may not yet be full agreement.

The mention of specific companies or of certain manufacturers' products does not imply that they are endorsed or recommended by the World Health Organization in preference to others of a similar nature that are not mentioned. Errors and omissions excepted, the names of proprietary products are distinguished by initial capital letters.

The World Health Organization does not warrant that the information contained in this publication is complete and correct and shall not be liable for any damages incurred as a result of its use.

WHOQOL-BREF

The following questions ask how you feel about your quality of life, health, or other areas of your life. I will read out each question to you, along with the response options. **Please choose the answer that appears most appropriate.** If you are unsure about which response to give to a question, the first response you think of is often the best one.

Please keep in mind your standards, hopes, pleasures and concerns. We ask that you think about your life **in the last four weeks**.

		Very poor	Poor	Neither poor nor good	Good	Very good
1.	How would you rate your quality of life?	1	2	3	4	5

		Very dissatisfied	Dissatisfied	Neither satisfied nor dissatisfied	Satisfied	Very satisfied
2.	How satisfied are you with your health?	1	2	3	4	5

The following q	juestions ask abo	ut how muc	h you have	experienced	certain th	ings in the last
four weeks.						

		Not at all	A little	A moderate amount	Very much	An extreme amount
3.	To what extent do you feel that physical pain prevents you from doing what you need to do?	5	4	3	2	1
4.	How much do you need any medical treatment to function in your daily life?	5	4	3	2	1
5.	How much do you enjoy life?	1	2	3	4	5
6.	To what extent do you feel your life to be meaningful?	1	2	3	4	5

		Not at all	A little	A moderate amount	Very much	Extremely
7.	How well are you able to concentrate?	1	2	3	4	5
8.	How safe do you feel in your daily life?	1	2	3	4	5
9.	How healthy is your physical environment?	1	2	3	4	5

	-		1			
		Not at all	A little	Moderately	Mostly	Completely
10.	Do you have enough energy for everyday life?	1	2	3	4	5
11.	Are you able to accept your bodily appearance?	1	2	3	4	5
12.	Have you enough money to meet your needs?	1	2	3	4	5
13.	How available to you is the information that you need in your day-to-day life?	1	2	3	4	5
14.	To what extent do you have the opportunity for leisure activities?	1	2	3	4	5

The following questions ask about how completely you experience or were able to do certa	ain
things in the last four weeks.	

		Very poor	Poor	Neither poor nor good	Good	Very good
15.	How well are you able to get around?	1	2	3	4	5

		Very dissatisfied	Dissatisfied	Neither satisfied nor dissatisfied	Satisfied	Very satisfied
16.	How satisfied are you with your sleep?	1	2	3	4	5
17.	How satisfied are you with your ability to perform your daily living activities?	1	2	3	4	5
18.	How satisfied are you with your capacity for work?	1	2	3	4	5
19.	How satisfied are you with yourself?	1	2	3	4	5

20.	How satisfied are you with your personal relationships?	1	2	3	4	5
21.	How satisfied are you with your sex life?	1	2	3	4	5
22.	How satisfied are you with the support you get from your friends?	1	2	3	4	5
23.	How satisfied are you with the conditions of your living place?	1	2	3	4	5
24.	How satisfied are you with your access to health services?	1	2	3	4	5
25.	How satisfied are you with your transport?	1	2	3	4	5

The following question refers to how often you have felt or experienced certain things in the last four weeks.

		Never	Seldom	Quite often	Very often	Always
26.	How often do you have negative feelings such as blue mood, despair, anxiety, depression?	5	4	3	2	1

Do you have any comments about the assessment?

[The following table should be completed after the interview is finished]

		Equations for commuting domain scores	Raw score	Transformed scores*	
		Equations for computing domain scores	Raw score	4-20	0-100
27.	Domain 1	(6-Q3) + (6-Q4) + Q10 + Q15 + Q16 + Q17 + Q18		b:	c:
			a. =		
28.	Domain 2	Q5 + Q6 + Q7 + Q11 + Q19 + (6-Q26)		b:	c:
			a. =		
29.	Domain 3	Q20 + Q21 + Q22		b:	c:
			a. =		
30.	Domain 4	Q8 + Q9 + Q12 + Q13 + Q14 + Q23 + Q24 + Q25		1	
			a. =	b:	c:

* See Procedures Manual, pages 13-15

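### The attached WHOQOL-BREF form prints items 3, 4 and 26 already reverse-coded and its Domain 1 and 2 equations reverse them again, so entering the printed codes scores these items backwards

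*Combined protocol and SAP*

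**What the plan says.** Section 2.5 (Design Summary) lists QOL among the endpoints. Section 3.1 gives no scoring method and sends the reader to the form: "QOL Survey is included in Chapter 4.2".

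On the form in section 4.2, the printed codes for the relevant items are:

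- Item 3, "To what extent do you feel that physical pain prevents you from doing what you need to do": *Not at all* = 5, down to *An extreme amount* = 1.
- Item 4, "How much do you need any medical treatment to function in your daily life": the same, 5 down to 1.
- Item 5, "How much do you enjoy life", in the same table under the same response labels: *Not at all* = 1, up to *An extreme amount* = 5. Item 6 also runs 1 to 5.
- Item 26, "How often do you have negative feelings such as blue mood, despair, anxiety, depression": *Never* = 5, down to *Always* = 1.

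At the end of the form comes the instruction "The following table should be completed after the interview is finished", followed by the domain equations. Domain 1 is "6-Q3) + (6-Q4) + Q10 + Q15 + Q16 + Q17 + Q18" (the opening bracket before the first 6 is left out of the quote). Domain 2 is "Q5 + Q6 + Q7 + Q11 + Q19 + (6-Q26" (closing bracket left out). A footnote on the transformed scores points to a procedures manual that is not part of the documents.

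**The concern.** Each negatively worded item has to be reversed once, either in the printed codes or in the equation. The form does it in both places. The descending codes are not a PDF reading error: items 5 and 6 sit in the same table as items 3 and 4 and ascend, and the only three items that descend are the three that the equations subtract from 6.

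The printed codes are the only numbers the form offers for these answers, so the natural course is to put them into the equations once the interview is over. Items 3, 4 and 26 would then count in the wrong direction: less pain, less need for treatment and fewer negative feelings would lower the score. A treatment difference spread evenly over the items would be shrunk in both domains. With 10 patients per arm (section 2.3) there is little signal to lose, and blinding the analyst to group gives no protection against a scoring error.

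**Working it through.** **Inputs.** Printed item codes and domain equations from section 4.2. No sample size, power or alpha figure is involved, and the plan states no score to reproduce.

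**Notation.** Q is the printed code (higher = better). S is the sum of the other five Domain 1 items (10, 15, 16, 17, 18). T is the sum of the other five Domain 2 items (5, 6, 7, 11, 19).

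- As printed: D1 = (6 − Q3) + (6 − Q4) + S; D2 = T + (6 − Q26).
- Reversed once: D1 = Q3 + Q4 + S; D2 = T + Q26.

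**Extreme answers, printed codes entered**

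| Answers | Domain | Equation as printed | Reversed once |
|---|---|---|---|
| All best (5) | 1 | 1 + 1 + 25 = 27 | 5 + 5 + 25 = 35 |
| All best (5) | 2 | 25 + 1 = 26 | 25 + 5 = 30 |
| All worst (1) | 1 | 5 + 5 + 5 = 15 | 1 + 1 + 5 = 7 |
| All worst (1) | 2 | 5 + 5 = 10 | 5 + 1 = 6 |

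**Error for any set of answers (as printed minus reversed once)**

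- Domain 1: 12 − 2(Q3 + Q4), from −8 to +8 on a span of 35 − 7 = 28. It is zero only when Q3 + Q4 = 6, which is 5 of the 25 possible answer pairs.
- Domain 2: 6 − 2 × Q26, from −4 to +4 on a span of 30 − 6 = 24. It is zero only at Q26 = 3, one of five answers.
- The possible raw range is 7–35 and 6–30 under either rule, so no wrong score falls out of range.

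**Effect on a change or a between-arm difference.** Let the double-reversed items improve by d categories each and the other items by e each.

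- Domain 1 moves by 5e − 2d instead of 5e + 2d. The sign flips if d > 2.5e.
- Domain 2 moves by 5e − d instead of 5e + d. The sign flips if d > 5e.
- Illustration with d = e = 1: Domain 1 moves by 3 instead of 7 (4/7 = 57% lost), Domain 2 by 4 instead of 6 (2/6 = 33% lost).
- Improvement of one category on items 3 and 4 alone moves Domain 1 by −2 instead of +2; on item 26 alone, Domain 2 moves by −1 instead of +1.

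**0–100 scale.** Assuming a linear rescaling, which the documents do not give: best answers score (27 − 7)/28 = 71.4 and (26 − 6)/24 = 83.3 instead of 100; worst answers score (15 − 7)/28 = 28.6 and (10 − 6)/24 = 16.7 instead of 0.

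**The other entry rule.** If responses are entered as 1 to 5 from left to right, best answers on the three items are coded 1. The printed equations then give 5 + 5 + 25 = 35 and 25 + 5 = 30, and for worst answers 1 + 1 + 5 = 7 and 5 + 1 = 6. The error is zero.

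Domains 3 and 4 contain none of the three items and are unaffected.

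**The case against.** The strongest reply is that the error depends on something the documents do not show. The form is read aloud, the participant picks a verbal answer, and no sentence tells staff to record the printed number, whereas the OSDI form in section 4.1 does tell them to circle the number. The instruction above the scoring table fixes when it is completed, not what goes into it. The database coding is not visible, and the data-entry sentence in section 2.4 is cut off in the copy available, so an entry rule may have been lost. All of this stands: the mismatch between codes and equations is certain, but its effect on the results is not.

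It is also fair that QOL carries little weight here. It is not named as primary, has no stated hypothesis and does not appear in the visit lists of section 2.4, and no text commits to comparing Domains 1 and 2 between arms. The conflict lies in an attached standard form, not in the investigators' own text. The same rule would apply to both arms, so it would not create a difference where responses are alike. The 57% and 33% figures assume an equal change on every item and are illustrative only.

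These points limit the severity without removing the problem. The protocol adopts the form and offers no other scoring rule, and following that rule with the only numbers on the form gives wrong scores. The manual reference does not help: it is attached to the transformed scores, not to the item codes or raw equations.

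**Conclusion.** The concern holds. As printed, the codes and the equations together reverse items 3, 4 and 26 twice. With printed codes entered, the raw error reaches 8 points out of a 28-point span in Domain 1 and 4 out of 24 in Domain 2. It pulls both ends of each scale towards the middle and cannot be seen from the ranges. The conclusion rests on one assumption, that the printed codes are what is entered; under entry by column position the error is nil. It should be fixed, but it touches two domains of one endpoint not named as primary, and it is reversible by rescoring as long as item-level responses and their entry coding are kept.

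**What to change.** First establish, from completed forms and the database set-up, whether items 3, 4 and 26 are recorded as the printed code or as column position. Do not alter the equations before that check, because doing so would create the error in data entered by position. Then apply exactly one reversal:

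- Printed codes entered: Domain 1 = Q3 + Q4 + Q10 + Q15 + Q16 + Q17 + Q18; Domain 2 = Q5 + Q6 + Q7 + Q11 + Q19 + Q26.
- Position 1 to 5 entered: keep the (6 − Q) terms.

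State the rule in section 4.2 and in the data file, keep item-level responses, and do not change the printed codes partway through the study. As a test of the scoring, all-best answers must return raw 35 and 30, and all-worst answers 7 and 6.

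The cost is one check of entry coding, one sentence in section 4.2 and, if needed, rescoring of two domains. No new data, visits or participants are required.
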